3.1 DESCRIPTION OF THE STUDY

This is a Phase II, multicenter, OLE study to evaluate the long-term safety and efficacy of GDC-0853 in patients with RA who have completed 12 weeks of study treatment in Study GA29350. The population for this study consists of patients with RA who have had an inadequate response to previous MTX therapy (Cohort 1 of Study GA29350) or previous TNF and MTX therapy (Cohort 2 of Study GA29350).

This OLE study will be conducted in centers that have participated in the double-blind, Phase II Study GA29350. The maximum number of patients potentially enrolling in this study will be approximately 580 patients. Patients will be assigned the same patient number they had in Study GA29350.

Eligible patients from Study GA29350 who elect to participate will receive treatment with GDC-0853 at 200 mg BID in an open-label fashion for 52 weeks, followed by a safety follow-up period of 8 weeks. Dose reductions of GDC-0853 to 200 mg QD are allowed for specific safety reasons (see Section 5.1.2) and may be allowed on the basis of clinical safety concerns of the investigator, only after discussion with the Medical Monitor. Eligible patients will be enrolled directly into Study GA30067 following treatment completion at Week 12 of Study GA29350 (e.g., they will not undergo the 8 weeks of safety follow-up in Study GA29350). The dose and route of administration of MTX at the end of the blinded Study GA29350 should be continued and held stable for the first 12 weeks of the OLE study. Discontinuation of MTX or alteration of the MTX dose prior to Week 12 is discouraged. Use of additional DMARDs other than MTX is discouraged prior to Week 12.

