3.3 RATIONALE FOR STUDY DESIGN

3.3.1 Rationale for GDC-0853 Dose and Schedule

In the event of a safety issue, dose reduction to 200 mg QD is permitted (see Section 5.1.2). This dose was selected because it is expected to reflect what may be a physician-initiated dose reduction in a real-world clinical setting (i.e., changing the dosing interval from BID to QD).

No safety or tolerability issues were identified in healthy subjects receiving GDC-0853 up to 600 mg in the single-dose Study GP29318 (SAD) and up to 250 mg BID and 500 mg QD for 14 days in the multiple-dose study GA29347 (MAD). No maximum tolerated dose was identified, and there were no dose-limiting adverse events; all adverse events were Grade 1 (mild) and transient.

Data from experiments evaluating the PD effects and anti-inflammatory activity of a tool BTK inhibitor compound (GDC-0834) in the rat model of CIA suggest that the amount of BTK inhibition anticipated in this study may be sufficient to achieve meaningful anti-inflammatory activity. These studies suggest that 70% BTK inhibition, as measured by phospho-BTK inhibition, is required for half-maximal activity (Liu et al. 2011). However, it is not known whether BTK inhibition in the rat CIA model accurately predicts efficacy in human RA.

Dose levels in this study are anticipated to result in exposures below 10 μ M • h (mean AUC₀₋₂₄), which is the NOAEL from nonclinical toxicology studies. The NOAEL (10 μ M • h) was defined in the 4-week dog study by vasculitis at higher doses (\geq 56 μ M • h). In the ongoing 9-month dog study, no vasculitis was observed up to the highest dose tested (37 μ M • h); however, 1 of 4 dogs at the highest dose had seminiferous tubule degeneration in the testis; a 4-month recovery phase is in progress. No testicular findings have been observed at lower doses (\leq 10 μ M • h). For further details, see the GDC-0853 Investigator's Brochure.

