4.2.2.1 GDC-0853 Dose and Administration

The GDC-0853 dose regimen is oral 200 mg BID. Patients will receive GDC-0853 approximately every 12 hours for 52 weeks. Patients should be directed to take one dose (a total of 4 tablets) BID (total of 8 tablets each day). On clinic visit days during the first 12 weeks of the study, patients should be instructed that the a.m. dose of GDC-0853 will be administered in the clinic, except for Day 1, since the last dose of GDC-0853 for Study GA29350 is the a.m. dose on Day 84 for all patients. For patients continuing into the OLE Study GA30067, the first open-label dose of GDC-0853 should be the p.m. dose (may be taken at home) on Day 84 (which is Day 1 of Study GA30067). After Week 12, GDC-0853 administration in the clinic is not required.

A dose reduction of GDC-0853 for specific safety events is permitted (see Table 3). For a potential dose reduction for other adverse events not listed in the table, please consult the Medical Monitor. If dose reduction is indicated, the dose of GDC-0853 may be reduced from 200 mg BID to 200 mg QD. In this case, patients should be directed to take one dose (a total of 4 tablets) QD in the morning (total of 4 tablets each day).

Guidelines for dose reduction and treatment interruption or discontinuation are provided in Section 5.1.

GDC-0853 may be orally administered with or without food. The dates and times of the most recent prior meal, last dose of GDC-0853 (prior to clinic visit), and timing of GDC-0853 administration in clinic should be recorded at each clinic visit. In addition, any use of PPIs, H2-receptor antagonists (H2RAs), and/or other antacids (e.g., Maalox®, Pepto-Bismol®, Rolaids®) should be recorded as concomitant medications, including time and date of last administration. Administration of GDC-0853 should be staggered with antacid use (i.e., GDC-0853 should be taken 2 hours before or 2 hours after the antacid).

GDC-0853—Genentech, Inc. 51/Protocol GA30067, Version 2

At study visits, sufficient GDC-0853 tablets will be dispensed to complete dosing until the next scheduled visit. When GDC-0853 is administered at the site, it will be administered under supervision of study personnel, and the amount of GDC-0853 dispensed must be recorded.

4.2.2.2 *GDC-0853 Compliance*

The following measure will be taken to assess patient compliance with study drug: patients will be directed to bring any used and unused bottles to each visit.

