Grade 3: ANC 500–1000/mm ³	For the first occurrence of a Grade 3 neutrophil count decreased, withhold GDC-0853 and recheck the CBC in 7 days. If the neutrophil count has recovered to Grade 1 (>1500/mm³) or normal range, resume dosing at 200 mg BID. If the Grade 3 neutropenia persists, discontinue GDC-0853. Second occurrence of Grade 3 neutrophil count decreased: Withhold GDC-0853, recheck CBC in 7 days. If the
	neutrophil count has recovered to Grade 1 (>1500/mm³) or normal range, restart GDC-0853 at the lower dose of 200 mg QD. If the Grade 3 neutrophil count decreased persists, discontinue GDC-0853.
	Third occurrence of Grade 3 neutrophil count decreased: Discontinue GDC-0853.
Grade 4: ANC < 500/mm ³	For Grade 4 neutrophil count decreased: discontinue GDC-0853.
Thrombocytopenia ^d	
Grade 1: PLT > 75,000/mm ³	In the absence of bleeding event(s), maintain GDC-0853 dosing.
Grade 2: PLT 50,000-75,000/mm	First occurrence of Grade 2 platelet count decreased: withhold GDC-0853, recheck CBC in 7 days. If platelet count has recovered to Grade 1 or has returned to the normal range, and in the absence of bleeding resume dosing at 200 mg BID.
	Second occurrence of Grade 2 platelet count decreased: withhold GDC-0853, recheck CBC in 7 days. If platelet count has recovered to Grade 1 or has returned to the normal range and in the absence of bleeding restart GDC-0853 at the lower dose of 200mg QD.
	Third occurrence of Grade 2 platelet count decreased: Discontinue GDC-0853.

Table 3 Guidelines for Management of GDC-0853 in Patients Who Experience Specific Adverse Events (cont.)

Event	Action to Be Taken ^a
Grade ≥ 3: PLT < 50,000/mm ³	For Grade 3 or greater platelet count decreased: discontinue GDC-0853.
Gastrointestinal effects	
Nausea, vomiting, and/or diarrhea	Manage according to site institutional guidelines. Consider administration of GDC-0853 with food as possible mitigation strategy.
	Consider reducing GDC-0853 dose to 200 mg QD and discuss with Medical Monitor.
Malignancy	
Any malignancy (with the exception of non-serious local and resectable basal or squamous cell carcinoma of the skin).	Discontinue GDC-0853. Report event as an adverse event of special interest to the Sponsor in an expedited manner.
Hepatotoxicity	
Any AST or ALT $> 3.0-5.0 \times ULN$	Withhold GDC-0853 and consult with the Medical Monitor.
AST or ALT elevation >3×ULN in	Discontinue GDC-0853.

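### Table 3 restarts every first Grade 3 neutropenia and first Grade 2 thrombocytopenia at 200 mg BID, which doubles the dose of a patient already reduced to 200 mg QD

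*Combined protocol and SAP*

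**What the plan says.** The assigned regimen is 200 mg BID (Section 4.2.2.1). Table 3 in Section 5.1.2 sets a ladder for each cytopenia and counts occurrences separately for neutrophils and platelets.

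- **First Grade 3 neutropenia** (ANC 500–1000/mm³): withhold, recheck in 7 days; on recovery to Grade 1 "or normal range, resume dosing at 200 mg BID. If the Grade 3 neutropenia persists, discontinue GDC-0853".
- **First Grade 2 thrombocytopenia** (platelets 50,000–75,000/mm³): withhold, recheck in 7 days; on recovery and "in the absence of bleeding resume dosing at 200 mg BID".
- **Second occurrence**: on recovery, the neutropenia row says "restart GDC-0853 at the lower dose of 200 mg QD", and the platelet row says "in the absence of bleeding restart GDC-0853 at the lower dose of 200mg QD".
- **Third occurrence**: discontinue.

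The protocol also provides for patients on the lower dose for other reasons. The gastrointestinal row of Table 3 says "Consider reducing GDC-0853 dose to 200 mg QD and discuss with Medical Monitor". Section 3.1 adds that a reduction "may be allowed on the basis of clinical safety concerns of the investigator, only after discussion with the Medical Monitor". Section 3.3.1 states: "In the event of a safety issue, dose reduction to 200 mg QD is permitted". Section 4.2.2.1 says that, where reduction is indicated, "the dose of GDC-0853 may be reduced from 200 mg BID to 200 mg QD". The dosing footnote in Appendix 1 makes BID dosing subject to an exception for patients whose dose has been reduced.

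**The concern.** The two first-occurrence rows name an absolute dose. That is right for a patient who was on BID when the event began. For a patient who was on QD it is an increase. A site following the row would then undo a reduction made for safety, and would do so just after a further toxicity serious enough to require a hold.

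The rows do not require the Medical Monitor to be consulted before restart, although the rows for treated non-serious infection, serious bleeding, gastrointestinal effects and moderate transaminase elevation do call for the Medical Monitor's involvement. They require a blood count before restart but none after it. After Week 12 the scheduled hematology visits are at Weeks 24, 36 and 52 (Appendix 1), so 12 to 16 weeks can pass before the next routine count. Cytopenias are a named risk of the drug (Section 5.1.1.4). Sites could also differ, some following the named dose and others keeping the patient on QD.

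**Working it through.** **1. The plan's dose figures.** Tablets are 50 mg (Section 4.2.1). Section 4.2.2.1 gives 4 tablets per dose, hence 8 tablets a day on BID and 4 on QD.

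- BID: 4 × 2 = 8 tablets; 8 × 50 mg = 400 mg/day.
- QD: 4 × 1 = 4 tablets; 4 × 50 mg = 200 mg/day.
- Ratio: 400 / 200 = 2.0.

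The tablet counts match those stated in the protocol.

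**2. Can a patient be on QD at a first cytopenia?** Yes, by three routes:

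- gastrointestinal effects (Table 3);
- another safety concern, with Medical Monitor involvement (Sections 3.1, 4.2.2.1, 5.1, 5.1.2);
- a second occurrence in the other cell line (Table 3 alone).

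The third route exists because each cytopenia has its own occurrence count.

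**3. A sequence that uses Table 3 only.** The ANC values are illustrative.

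| Event | Row that applies | Restart dose, as written | Restart dose, with the fix |
|---|---|---|---|
| Platelets Grade 2, recover | Thrombocytopenia, first | 400 mg/day | 400 mg/day |
| Platelets Grade 2 again, recover | Thrombocytopenia, second | 200 mg/day | 200 mg/day |
| ANC 800/mm³, then 1700/mm³ at day 7 | Neutropenia, first | 400 mg/day | 200 mg/day |

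The reverse order (two Grade 3 neutropenias, then a first Grade 2 thrombocytopenia) gives the same doses: 400, 200, 400 as written and 400, 200, 200 with the fix.

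**4. Does other text close the gap?** Sections 3.1, 3.3.1, 4.2.2.1, 5.1 and 5.1.2 and the Table 3 footnotes were read for any statement that a reduction is permanent, that re-escalation is barred, or that dosing resumes at the previous level. None was found. The Appendix 1 exception shows that reduced patients were foreseen, but it is a general footnote and the two rows do not carry it.

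**5. Who is concerned?** Only patients with ANC 500–1000/mm³ or platelets 50,000–75,000/mm³. Grade 4 neutropenia and Grade 3 or greater thrombocytopenia lead to discontinuation (Section 4.5.2). Entry excludes ANC below 1.5 × 10⁹/L and platelets below 100 × 10⁹/L (Section 4.1.2). The documents give no rate for a prior reduction followed by a first cytopenia, so no patient count can be derived.

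**The case against.** The best counter-argument is that the rows were plainly written for patients on BID. To resume is to return to what was being taken, and the reference to a lower dose in the second-occurrence rows makes sense only for someone coming from BID. Section 4.2.2.1 sets no end date for a reduction, and Appendix 1 excepts reduced patients in general terms. Table 3 is headed as guidelines, and most routes to QD already involve the Medical Monitor, who would know that the patient had been reduced. The one route that does not needs three separate cytopenia events across two cell lines within 52 weeks.

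Much of this stands. The intent was very probably BID at onset, and the case is rare. But the rows state a specific dose, and a general footnote does not clearly override a specific instruction. Keeping the patient on QD would depart from the row's wording, and on the cross-cell-line route the cytopenia rows themselves require no consultation.

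Two objections concern the remedy. The first is that barring re-escalation would make every reduction permanent, including one for nausea that has since resolved. It would not: the wording governs only the restart after a new cytopenia. The second is that a patient on QD at a second occurrence would restart at QD with no further reduction. That is true and is left as it is; that patient's dose is not raised, so the error described here does not arise.

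**Conclusion.** The point holds and is minor. On the literal text, a patient on 200 mg QD at a first Grade 3 neutropenia or first Grade 2 thrombocytopenia restarts at 400 instead of 200 mg/day, a two-fold difference.

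The consequence is limited. 400 mg/day is the assigned dose, and patients on BID with the same event also restart at it. Restart needs count recovery and, for platelets, no bleeding. Adverse event follow-up (Section 5.5.1) and unscheduled visits (Section 4.4.11) remain available. No planned analysis changes, because safety is summarised descriptively by parent-study cohort (Sections 6 and 6.4).

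The conclusion rests on two assumptions: that sites apply the row as worded, and that no withheld text supplies a restart rule. Section 3.3.1 opens abruptly, so its silence on returning to BID carries little weight by itself. The number of patients affected is not given and is likely small.

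**What to change.** In both first-occurrence rows of Table 3, replace the fixed BID restart dose with: *resume at the dose taken before the interruption (do not re-escalate a patient on 200 mg QD)*. Patients on BID at onset are managed exactly as now. The cost is wording in two table rows, which can go into the next amendment, with no added visits, tests or patients.

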5.2 SAFETY PARAMETERS AND DEFINITIONS

Safety assessments will consist of monitoring and recording adverse events, including serious adverse events and adverse events of special interest, performing protocol-specified safety laboratory assessments, measuring protocol-specified vital signs, and conducting other protocol-specified tests that are deemed critical to the safety evaluation of the study.

Certain types of events require immediate reporting to the Sponsor, as outlined in Section 5.4.

5.2.1 Adverse Events

According to the ICH guideline for Good Clinical Practice, an adverse event is any untoward medical occurrence in a clinical investigation patient administered a pharmaceutical product, regardless of causal attribution. An adverse event can therefore be any of the following:

- Any unfavorable and unintended sign (including an abnormal laboratory finding), symptom, or disease temporally associated with the use of a medicinal product, whether or not considered related to the medicinal product
- Any new disease or exacerbation of an existing disease (a worsening in the character, frequency, or severity of a known condition), except as described in Section 5.3.5.10
- Recurrence of an intermittent medical condition (e.g., headache) not present at haseline
- Any deterioration in a laboratory value or other clinical test (e.g., ECG, X-ray) that is
 associated with symptoms or leads to a change in study treatment or concomitant
 treatment or discontinuation from study drug
- Adverse events that are related to a protocol-mandated intervention, including those that occur prior to assignment of study treatment (e.g., screening invasive procedures such as biopsies)

5.2.2 Serious Adverse Events (Immediately Reportable to the Sponsor)

A serious adverse event is any adverse event that meets any of the following criteria:

- Is fatal (i.e., the adverse event actually causes or leads to death)
- Is life threatening (i.e., the adverse event, in the view of the investigator, places the patient at immediate risk of death)

This does not include any adverse event that had it occurred in a more severe form or was allowed to continue might have caused death.

Requires or prolongs inpatient hospitalization (see Section 5.3.5.11)

- Results in persistent or significant disability/incapacity (i.e., the adverse event results in substantial disruption of the patient's ability to conduct normal life functions)
- Is a congenital anomaly/birth defect in a neonate/infant born to a mother exposed to study drug
- Is a significant medical event in the investigator's judgment (e.g., may jeopardize the patient or may require medical/surgical intervention to prevent one of the outcomes listed above)

The terms "severe" and "serious" are not synonymous. Severity refers to the intensity of an adverse event (e.g., rated as mild, moderate, or severe, or according to NCI CTCAE; see Section 5.3.3); the event itself may be of relatively minor medical significance (such as severe headache without any further findings).

Severity and seriousness need to be independently assessed for each adverse event recorded on the eCRF.

Serious adverse events are required to be reported by the investigator to the Sponsor immediately (i.e., no more than 24 hours after learning of the event; see Section 5.4.2 for reporting instructions).

5.2.3 Adverse Events of Special Interest (Immediately Reportable to the Sponsor)

Adverse events of special interest are required to be reported by the investigator to the Sponsor immediately (i.e., no more than 24 hours after learning of the event; see Section 5.4.2 for reporting instructions). Adverse events of special interest for this study include the following:

Adverse Events of Special Interest for GDC-0853:

- Any serious infection, any infections requiring IV antimicrobials (i.e., Grade 3 infection) and any opportunistic infections
- Any bleeding event Grade 2 or above
- All malignancies
- A laboratory result of an AST or ALT elevation of Grade ≥ 3 (i.e., AST or ALT >5×ULN)

Adverse Events of Special Interest for General Drug Development:

- Cases of potential drug-induced liver injury that include an elevated ALT or AST in combination with either an elevated bilirubin or clinical jaundice, as defined by Hy's law (see Section 5.3.5.6)
- Suspected transmission of an infectious agent by the study drug, as defined below:

Any organism, virus, or infectious particle (e.g., prion protein transmitting transmissible spongiform encephalopathy), pathogenic or non-pathogenic, is

considered an infectious agent. A transmission of an infectious agent may be suspected from clinical symptoms or laboratory findings that indicate an infection in a patient exposed to a medicinal product. This term applies only when a contamination of the study drug is suspected.

5.3 METHODS AND TIMING FOR CAPTURING AND ASSESSING SAFETY PARAMETERS

The investigator is responsible for ensuring that all adverse events (see Section 5.2.1 for definition) are recorded on the Adverse Event eCRF and reported to the Sponsor in accordance with instructions provided in this section and in Sections 5.4–5.6.

For each adverse event recorded on the Adverse Event eCRF, the investigator will make an assessment of seriousness (see Section 5.2.2 for seriousness criteria), severity (see Section 5.3.3), and causality (see Section 5.3.4).

5.3.1 Adverse Event Reporting Period

Investigators will seek information on adverse events at each patient contact. All adverse events, whether reported by the patient or noted by study personnel, will be recorded in the patient's medical record and on the Adverse Event eCRF.

After informed consent has been obtained but prior to initiation of study drug, only serious adverse events caused by a protocol-mandated intervention (e.g., invasive procedures such as biopsy sample collections, discontinuation of medications) should be reported (see Section 5.4.2 for instructions for reporting serious adverse events).

After initiation of study drug, all adverse events will be reported until 8 weeks after the last dose of study drug the patients receives. After this period, the investigator should report any serious adverse events that are believed to be related to prior study drug treatment (see Section 5.6).

5.3.2 Eliciting Adverse Event Information

A consistent methodology of non-directive questioning should be adopted for eliciting adverse event information at all patient evaluation timepoints. Examples of non-directive questions include the following:

"How have you felt since your last clinic visit?"

"Have you had any new or changed health problems since you were last here?"

5.3.3 Assessment of Severity of Adverse Events

The adverse event severity grading scale for the NCI CTCAE (v4.0) will be used for assessing adverse event severity. Table 4 will be used for assessing severity for adverse events that are not specifically listed in the NCI CTCAE.

Table 4 Adverse Event Severity Grading Scale for Events Not Specifically Listed in NCI CTCAE

Grade	Severity
1	Mild; asymptomatic or mild symptoms; clinical or diagnostic observations only; or intervention not indicated
2	Moderate; minimal, local, or non-invasive intervention indicated; or limiting age-appropriate instrumental activities of daily living ^a
3	Severe or medically significant, but not immediately life-threatening; hospitalization or prolongation of hospitalization indicated; disabling; or limiting self-care activities of daily living b,c
4	Life-threatening consequences or urgent intervention indicated d
5	Death related to adverse event ^d

NCI CTCAE=National Cancer Institute Common Terminology Criteria for Adverse Events. Note: Based on the most recent version of NCI CTCAE (v4.0), which can be found at: http://ctep.cancer.gov/protocolDevelopment/electronic applications/ctc.htm

- ^a Instrumental activities of daily living refer to preparing meals, shopping for groceries or clothes, using the telephone, managing money, etc.
- ^b Examples of self-care activities of daily living include bathing, dressing and undressing, feeding oneself, using the toilet, and taking medications, as performed by patients who are not bedridden.
- ^c If an event is assessed as a "significant medical event," it must be reported as a serious adverse event (see Section 5.4.2 for reporting instructions), per the definition of serious adverse event in Section 5.2.2.
- Grade 4 and 5 events must be reported as serious adverse events (see Section 5.4.2 for reporting instructions), per the definition of serious adverse event in Section 5.2.2.

